Administration of obinutuzumab ^x	X ^x																				
Obinutuzumab PK Sample ^x	X ^x	X				X ^u		X						X ^y				X			
ADA to obinutuzumab	X													X ^y							
Administration of RO7172508 ^l		X ^j						X ^j						X ^j							
RO7172508 PK Sample		X	X	X	X	X	X	X	X	X	X	X	X		X	X		X	X		X
ADA to RO7172508		X				X	X	X				X	X	X				X	X		X
sCEA	X ^z	X	X	X	X	X	X	X	X	X	X	X	X		X			X	X		X

Table 2 Part II: Multiple Participant Cohorts IV Q3W/Multiple Ascending Dose-Escalation (cont.)

Cycle (21 days)	Screening	Cycle 1 - 2						Cycle 3 - 4 ^a				Cycle 5 onwards ^a			End of Treatment	Safety Follow-Up	Survival Follow-Up ^q	Unscheduled (Safety)				
Day	D-28 to D-1	Day 1	Day 2	Day 3	Day 8	Day 15	Day 1	Day 3 ^p	Day 8	Day 15	Day 1	Day 3 ^{c, p}	Day 15									
Assessments ^a		pre-dose	EOI +15 mins	2 hrs EOI ±15 mins	24 hrs EOI ±2 hrs	48 hrs EOI ±4 hrs					pre-dose	EOI +15 mins	2 hrs EOI ±15 mins	48 hrs EOI ±1 day				incl. early discontin. visit e.g. progressive disease	60 Days after last treatment (± 5 Days)	90 Days after last treatment then every 3 mths ^q	e.g. In the event of an IRR ≥G2 ^o	
PD Blood Flow Cytometry		X			x		X				X				x ^{aa}			x				
PD Blood Cytokines		X	X	X	X	X	X	X	X	X	X	X	X		X ^m	X ^t	X ^m		X			X ^o
TCR Vβ ^k		X ^k													X ^k							
CtDNA/tumor markers		X ^k													X ⁿ							
Clinical Genotyping		X ^u																				
RBR Sample (DNA)		X ^u																				
RBR Sample (RNA)		X ^u													X ⁿ							
IgE & Tryptase																						X ^o

Notes: ADA=anti-drug antibody; AE=adverse event; C=Cycle; CEA=carcinoembryonic antigen; ct=circulating tumor; D=day; discontin=discontinuation;

DNA=deoxyribonucleic acid; ECG=electrocardiogram; ECOG=Eastern Cooperative Oncology Group; G2=grade 2; HIV=human immunodeficiency virus;

IgE=immunoglobulin E; incl=including; IRR=infusion related reaction; PD=pharmacodynamics; PK=pharmacokinetic; RBR=Research Biosample Repository;

RECIST=Response Evaluation Criteria in Solid Tumors; RNA=ribonucleic acid; sCEA = soluble CEA; TCR = T cell receptor.

- All visits from Cycle 3 onwards should occur within a 3-day time window, unless otherwise indicated and all assessments or samples where indicated should be taken prior to the administration of RO7172508.
- Informed consent must be obtained before any study-specific procedures *and may be obtained > 28 days before the start of study treatment.*
- Visit to be done only every second cycle after Cycle 5. (i.e. C7, C9 etc.).

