- 12-lead ECG at screening (within one week before first dose of RO7172508). After Cycle 4, 12-lead ECG to be done only at every second cycle (i.e. Cycle 6, Cycle 8 etc.). Additional unscheduled ECG assessments in triplicate should be performed in case of abnormalities and if clinical symptoms occur. Recording must be done prior to PK sampling.

Table 2 Part II: Multiple Participant Cohorts IV Q3W/Multiple Ascending Dose-Escalation (cont.)

- e) Serum pregnancy test at screening, within 7 days prior to first dose, and at the safety follow-up visit; a urine pregnancy test will be performed at specified subsequent visits. If a urine pregnancy test is positive, it must be confirmed by a blood pregnancy test. Results must be obtained and reviewed prior to administration of RO7172508.
- f) Hematology, blood chemistry, coagulation, and urinalysis can be performed within 24 hours (up to 72 hours if during weekend) prior to scheduled dosing. Screening results can be within 1 week prior to C1D1. Results must be obtained and reviewed prior to administration of RO7172508.
- g) Tumor biopsy samples will be collected during screening, once during the study treatment period at Cycle 2 Day 8 and optionally at the end of treatment visit ONLY if the reason for discontinuation is progressive disease. If a fresh biopsy is performed for screening purposes, this can be used as the baseline sample.
- h) As part of the eligibility procedure, CEA expression will be confirmed on archival tumor material, *with the exception of CRC participants*. If no archival tumor sample is available, fresh sample will be collected and be assessed (the same sample would constitute as baseline screening sample if participant is enrolled). Archival tissue should be submitted for additional biomarker assessments for all participants (if available).
- i) Tumor response is assessed by the Investigator per RECIST V1.1 with the use of physical examination and image-based evaluation. All measurable and evaluable lesions should be assessed and documented during the screening period, within 7 days before Cycle 3 Day 1, thereafter every 6 weeks (± 7 days) for 12 weeks, and then every 12 weeks (± 7 days) until disease progression or death. (i.e. screening, C3, C5, C7, C11, C15, C19 etc.).
- j) All planned assessments are to be performed before administration of RO7172508. At least 24 hours (overnight) hospital stay required following administration of study drug at Cycle 1 Day 1.

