- l To allow estimation of tumor growth rate before start of treatment an exploratory assessment of tumor kinetics will be made by comparing post treatment scans with at least 2 pre-treatment scans not older than 12 weeks prior to C1D1 if available. One of the pre-treatment scans will be the study baseline scan taken during screening and the second will be within the preceding 12 weeks.*
- m Obinutuzumab to be administered either on Day-7 (2000 mg) or on Day-7 and Day-6 (1000 mg each day). If obinutuzumab is given only on one day, then the schedule for Day-7 should be followed including an end of infusion sample.*
- n Samples should be taken BEFORE obinutuzumab is administered.*
- o sCEA to be assessed for enrollment in cohorts with RO7172508 doses < 12 mg.*
- p Sample to be taken end of infusion only*

Table 7 Schedule of Assessments Part II: Multiple Participant Cohorts SC Q3W

Cycle (21 days)	Screening ^x	Cycle 1 - 2						Cycle 3 - 4 ^a				Cycle 5 onwards ^a			End of Treatment	Safety Follow-Up	Survival Follow-Up ^q	Unscheduled (Safety)	
Day	D-28 to D-1	Day 1	Day 2	Day 3	Day 5	Day 8	Day 15	Day 1	Day 3 ^p	Day 8	Day 15	Day 1	Day 3 ^{c, p}	Day 15					
Assessments ^a		pre-dose	24 hrs +/- 2 hrs	48 hrs +/- 4 hrs	+/- 1 day			pre-dose	48 hrs +/- 1 day			pre-dose	48hrs +/- 4 hrs		incl. early discont. visit (e.g. progressive disease)	60 Days after last treatment (+/- 5 Days)	90 Days after last treatment then every 3 mths ^q	e.g. In the event of an IRR ≥G2 ^o	
Informed Consent ^b	x																		
Eligibility	x																		
Demography	x																		
Medical History	x																		
Pulmonary Function Tests ^w	x																		
Archival Tissue ^h	x																		
Previous and Concomitant Treatments	x	x	x	x	x	x	x	x	x	x	x	x	x	x	x	x	x	x	x
Adverse Events	x	x	x	x	x	x	x	x	x	x	x	x	x	x	x	x	x	x	x
Physical Examination	x	x						x				x			x	x			x
Anthropometric Measurements ^s	x	x						x				x			x	x			x
Vital Signs ^v	x	x	x	x	x	x	x	x	x	x	x	x	x	x	x	x			x

Table 7 Schedule of Assessments Part II: Multiple Participant Cohorts SC Q3W (cont.)

Cycle (21 days)	Screening ^x	Cycle 1 - 2						Cycle 3 - 4 ^a				Cycle 5 onwards ^a			End of Treatment	Safety Follow-Up	Survival Follow-Up ^q	Unscheduled (Safety)
Day	D-28 to D-1	Day 1	Day 2	Day 3	Day 5	Day 8	Day 15	Day 1	Day 3 ^p	Day 8	Day 15	Day 1	Day 3 ^{c, p}	Day 15				

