For the SC administration, the mCRM-EWOC model will be updated to account for the available IV administration participant data and the difference in exposure with added uncertainty, given that the different routes of administration could lead to different safety profile. Each cohort will enroll a minimum of 3 participants. Enrollment and dose-escalation rules (i.e., stopping rules and maximum allowed increments) in Part II SC will be the same as the ones applied in Part II IV. DLT window will be the same as in Part II IV but may be updated based on emerging data. The dose-escalation will continue as described until one of the pre-defined stopping criteria is satisfied (see Section 4.1.4) or the pre-determined sample size of 60 DLT-evaluable participants is reached, whichever comes first.

No intra-participant dose-escalation will be allowed in Part II.

The OBD (IV and SC) will be selected based on the overall clinical safety and activity, as well as available PK and PD data for RO7172508. *Data will be listed and summarized by dose group as described in the analysis section (see Section 9.4).*

Once a schedule, route of administration and OBD has been selected, and in case efficacy is observed during dose-escalation, disease-specific expansions may be opened to confirm these efficacy signals. The protocol will be amended in this case to describe treatment of these cohorts. *If one route of administration is not unequivocally superior, and a decision cannot be taken during or at the end of dose escalation, both routes of administration may be compared in disease specific expansions. Criteria for selection of a route of administration will then be added via the protocol amendment preceding the expansions, including endpoints.*

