6.1.1 Pre-medication

All pre-medications should be captured as concomitant medications in the participant's electronic Case Report Form (eCRF). If during dose-escalation Grade ≥ 2 IRRs/CRS or tumor inflammatory events occur in the majority of participants, the utility of prophylactic pre-medication with systemic corticosteroids in preventing such events may be tested using the regimen as outlined in [Table 14](#) (flat dosing) and [Table 15](#) (for fractionated dosing). If successful, this regimen will then be used in future cohorts.

In the event that the change in the route of administration from IV to SC does not mitigate the tumor inflammatory events or IRRs, then the same steroid regimen may be implemented as described in [Table 14](#) and [Table 15](#). These regimens are based on the expected duration of inflammatory events and they may be reduced or modified based on emerging data. *Also, they may be extended from Cycle 1 to subsequent cycles, in case tumor inflammation and/or IRR occur at later cycles.* Pre-medication may also include 1000 ml saline, 50 mg indomethacin (or equivalent non-steroidal anti-inflammatory [NSAID]), and 50 mg diphenhydramine (or equivalent H1 antagonist).

Table 14 Steroid Use on Cycle 1 of RO7172508 Infusion to be implemented in the event of frequent IRR/CRS or gastrointestinal RO7172508-related toxicity occurrence after first administration

Timing	Dose
C1D1: 4 to 6 hours before RO7172508 infusion	1 mg/kg methylprednisolone IV* 1 g paracetamol PO TID 2 mg loperamide PO
C1D1: approximately 2 hours after RO7172508 infusion	1 mg/kg methylprednisolone IV*
C1D2: approximately 24 hours post-RO7172508 EOI	1 mg/kg prednisone IV/PO* 1 g paracetamol PO TID 2 mg loperamide PO**
C1D3: approximately 48 hours post-RO7172508 EOI	0.5 mg/kg prednisone IV/PO* 1 g paracetamol PO TID
C1D4: approximately 72 hours post-RO7172508 EOI	0.5 mg/kg prednisone IV/PO* 1 g paracetamol PO TID

C: Cycle; D: Day; EOI: end of infusion; IV: intravenous; PO: oral; TID: 3 times a day.

* rounded up to next multiple of 10 mg (or equivalent doses of mid acting steroids)

** subsequent treatment with loperamide only to be given as clinically indicated

Table 15 Steroid Use on Cycle 1 of RO7172508 or gastrointestinal RO7172508-related toxicity to be implemented in the event of frequent IRR/CRS persisting despite dose fractionation

Timing	Dose

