9.4 STATISTICAL ANALYSES

The data will be analyzed by the Sponsor and/or designated Contract Research Organization (CRO). Any data analysis carried out independently by the Investigator should be submitted to the Sponsor before publication or presentation. The data will be summarized with respect to demographic and baseline characteristics, efficacy observations and measurements, safety observations and measurements, pharmacokinetic and biomarker measurements. Data will be summarized by cohort and regimen within each part and CEA level where applicable, *including the additional participants that may be enrolled in expanded cohorts (see Section 4.1.2.2)*. *Participants who receive only obinutuzumab but no dose of RO7172508 will be summarized separately.*

The baseline value of any variable will be defined as the last available value prior to the first administration of study treatment (RO7172508 or obinutuzumab (if applicable) as appropriate).

The following endpoints may be used to select a route of administration for further development: PD parameters including T-cell activation in blood and in the tumor; pharmacokinetic parameters such as AUC, C_{max} and half-life; tolerability and safety; as well as incidence of ADAs and their effect on exposure. Clinical efficacy will be considered, but is not expected to be a key criterion, as efficacy will likely be affected by parameters which cannot be controlled for in such small cohorts. Data will be listed and summarized by dose group as described in this analysis section. Analyses are exploratory in nature and no formal hypothesis testing will be performed.

If one route of administration is not unequivocally superior, and a decision cannot be taken during or at the end of dose escalation, both routes of administration will be compared in disease specific expansion. Criteria for selection of a route of administration will then be added via the amendment preceding the expansions, including endpoints.

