9.4.6 Pharmacodynamic Analyses

All PD parameters will be presented by listings and descriptive summary statistics separately by group or cohorts.

The PD analysis will be based on the availability of evaluable blood or tumor samples.

All PD parameters will be listed by participant and tabulated by dose-level/regimen and time-point. Descriptive statistics will be used in summarizing peripheral blood and tumor PD markers.

Absolute and percentage change from baseline will be calculated for the PD markers. Graphical techniques will be employed to better understand the relationship of the PD markers with dose and time. Correlations between PD markers, PK of RO7172508, and clinical response will be assessed through data tabulations and graphical techniques. The potential prognostic value of the PD markers may also be investigated.

Correlations between the CEA expression level and pharmacodynamics and efficacy outcomes will be explored using graphical and modelling techniques.

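### If steroid premedication is introduced, the baseline blood PD sample may be drawn before or after the steroid, so change from baseline by dose or route could mix steroid and drug effects

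*Combined protocol and SAP*

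**What the plan says.** **Baseline.** Section 9.4: "The baseline value of any variable will be defined as the last available value prior to the first administration of study treatment". A bracket extends this to RO7172508 or obinutuzumab, as appropriate. Premedication is recorded in the eCRF as concomitant medication (Section 6.1.1), so it does not close the baseline window.

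**Blood PD sampling without obinutuzumab.** In Tables 2, 3, 4 and 7 of Section 1.3, the rows for "PD Blood Flow Cytometry" and for blood cytokines have no screening entry. The Cycle 1 Day 1 pre-dose draw is the only one before treatment. Its timing is tied to RO7172508 alone: "all assessments or samples where indicated should be taken prior to the administration of RO7172508" and, in Table 2, "All planned assessments are to be performed before administration of RO7172508".

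**Steroid timing.** If prophylaxis is used, the first row of both Table 14 and Table 15 reads "C1D1: 4 to 6 hours before RO7172508 infusion", with 1 mg/kg IV methylprednisolone. Budesonide may also be agreed, starting 3 days before the first RO7172508 dose. Steroids continue to Cycle 1 Day 4 (Table 14) or Day 16 (Table 15).

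**With obinutuzumab.** Table 6 adds a Day -7 flow cytometry and cytokine draw, with the footnote "Samples should be taken BEFORE obinutuzumab is administered". Table 16 makes prednisolone 100 mg IV mandatory at least 60 minutes before that infusion.

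**Use of the data.** Section 9.4.6: "Absolute and percentage change from baseline will be calculated for the PD markers". The results are tabulated by dose level or regimen and time-point, and plotted against dose and time. Section 4.1.2.2: "The OBD (IV and SC) will be selected based on the overall clinical safety and activity, as well as available PK and PD data". Section 9.4 also lists T-cell activation in blood among the endpoints that may be used to choose a route.

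**The concern.** Two sites can both follow the schedule and record different things as baseline: one a steroid-free value, the other a value some hours after 1 mg/kg methylprednisolone. Both qualify under Section 9.4. The exclusion criteria keep out participants on regular steroids or immunosuppressants in the preceding 28 days, so the plan treats such exposure as relevant. It also orders other samples around other drugs: the biopsy before obinutuzumab, and a cytokine draw within 2 hours before tocilizumab (Table 5). The steroid premedication has no such anchor.

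Section 6.1.1 allows prophylaxis to be tested once Grade 2 or higher reactions or tumor inflammatory events affect most participants, and carries it into later cohorts if it succeeds. In an ascending design those cohorts would mostly be at higher doses. A change in the dose-PD picture at the level where steroids began could then be read as drug effect. The route comparison is exposed too. SC cohorts take up the steroid regimen only if SC does not itself mitigate the events, so premedicated IV cohorts could be set beside unpremedicated SC cohorts.

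**Working it through.** The plan gives no figure to reproduce here: there is no PD sample size, no hypothesis test and no stated steroid effect. The check compares the timing rules and then uses assumed values to show direction and range.

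**1. Order of events, premedicated cohort without obinutuzumab.**
- Methylprednisolone: 4 to 6 hours before the infusion (Tables 14 and 15).
- PD tubes: any time on Day 1 before the infusion (Table 2 footnotes).
- Baseline: last value before RO7172508 (Section 9.4).

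A draw before the steroid and a draw in the 4 to 6 hours after it satisfy all three rules. With obinutuzumab, the same reasoning applies to the Day -7 draw and the prednisolone. Section 9.4's wording also leaves open whether the Day -7 or the Day 1 value is the PD baseline.

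**2. Direction of the bias.** Suppose the drug has no effect, the steroid lowers the baseline value by a fraction s, and it lowers the post-dose value by a fraction r. Both are assumptions.

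Apparent change = (1 − r)/(1 − s) − 1

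| s | r = 0 | r = 10% | r = 30% | r = 50% |
|---|---|---|---|---|
| 0 (pre-steroid baseline) | 0% | −10.0% | −30.0% | −50.0% |
| 10% | +11.1% | 0% | −22.2% | −44.4% |
| 30% | +42.9% | +28.6% | 0% | −28.6% |
| 50% | +100.0% | +80.0% | +40.0% | 0% |

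For example, s = 30% with r = 0 gives 1/0.7 − 1 = +42.9%, and s = 10% with r = 50% gives 0.5/0.9 − 1 = −44.4%. The sign depends on whether the baseline or the post-dose sample is the more suppressed.

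**3. What the first row shows.** A pre-steroid baseline (s = 0) removes the spurious rise, but an apparent fall remains whenever the post-dose sample is drawn under steroid. Ordering the draw makes baselines comparable. It does not separate drug from on-treatment steroid.

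**4. How closely steroid use would follow dose.** Take the ten provisional levels of Table 9, one point each, and assume steroids start at one level and continue at every level above it. The correlation between steroid use (0/1) and ln(dose) is

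(mean ln dose with steroid − mean without) × √[p(1 − p)] / SD of ln dose,

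where p is the share of levels with steroid. Starting at 40 mg: (4.955 − 1.791) × 0.5 / 1.808 = 0.88. Starting at 3.2, 6.3, 12, 20, 40, 80, 150, 300 or 400 mg, it is 0.54, 0.71, 0.80, 0.85, 0.88, 0.86, 0.80, 0.68 and 0.48. Under that pattern, dose and steroid would be strongly but not fully confounded.

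**The case against.** The strongest objection is that a pre-steroid baseline is not clearly better. If post-dose samples are taken under steroid, a post-steroid baseline compares like with like and comes closer to the incremental drug effect. The diagonal of the table shows this: equal suppression gives 0%. This stands as an argument that moving the tube is not enough. It does not justify leaving the order open, because a mixture of pre- and post-steroid baselines answers neither question, and a pre-steroid value that was never drawn cannot be recovered.

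Other points also have weight. The secondary PD endpoint is tumor TILs, whose baseline is the screening biopsy; changes in blood cells and cytokines are listed as exploratory. Data are summarized by cohort and regimen, and premedication is captured and listed, so premedicated cohorts would be partly visible. That does not show the order of draw within a cohort, and the confounding lies between cohorts. With as few as 3 evaluable participants per cohort, a split by premedication will have small cells and will display the confounding rather than remove it. The Laboratory Manual, to which Section 8.6 refers for sampling procedures and which is not among the documents, may fix the order; the protocol does not.

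A reader might infer more than the documents support:
- **That steroids will enter at the higher doses.** Prophylaxis is conditional, and later cohorts can be de-escalated, SC or expansion cohorts. Participants with an earlier Grade 2 reaction should also be premedicated at later infusions whatever their dose.
- **That PD change would be inflated.** A rise such as +100% needs 50% suppression of the baseline and none after dosing, whereas Tables 14 and 15 continue steroids after dosing.
- **That the Day 1 draw is always the only pre-treatment sample.** Under obinutuzumab, Table 6 adds Day -7.
- **That OBD selection would be misled.** The OBD is an overall judgment on safety, activity, PK and PD, with no formal PD rule.

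**Conclusion.** The gap is real and worth closing, but it is conditional. If steroid premedication is introduced, the plan lets the blood PD baseline fall on either side of the IV steroid and does not separate PD results by premedication. Baselines may then not be comparable between sites and cohorts, and blood PD by dose or route could mix steroid and drug effects in either direction. It could mislead OBD or route selection to the extent that blood PD weighs in those judgments.

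The size is unknown. The range of −50% to +100% rests on assumed suppression of 0 to 50% and no drug effect. The correlations of 0.48 to 0.88 rest on steroids starting at one Table 9 level and continuing upward. Tumor TIL baselines are outside this point, although the Cycle 2 Day 8 biopsy could still follow rescue steroids or tocilizumab.

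**What to change.** 1. **Schedule and baseline.** Add a footnote to Tables 2, 3, 4, 6 and 7: the existing Cycle 1 Day 1 and Day -7 PD flow cytometry and cytokine tubes are drawn before that day's IV corticosteroid premedication. State in Section 9.4 that the PD baseline is the Cycle 1 Day 1 sample without obinutuzumab and the Day -7 sample with it. If oral budesonide has already started, flag the baseline rather than add a visit.
2. **Analysis.** In Section 9.4.6, present PD by premedication status alongside dose, using the eCRF data already collected. Flag samples, including the Cycle 2 Day 8 biopsy, taken after rescue steroids or tocilizumab. State that a pre-steroid baseline alone does not remove on-treatment steroid effects.

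The cost is a draw some hours earlier on the same day and one more set of descriptive summaries, with small cells. No sample or visit is added, and no premedication regimen changes.
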